The pathogenesis of acne is multifactorial, involving a complex interplay between genetic predisposition, environmental exposures (e.g., humidity, pollution, comedogenic cosmetics), hormonal fluctuations, and immune dysregulation. The four classical pathogenic mechanisms include increased sebum production, abnormal follicular keratinization, colonization by *Cutibacterium acnes* and activation of innate and adaptive inflammatory responses (*Alsaadoon et al., 2024*). Although inflammation was once thought to occur secondary to microbial colonization, recent studies demonstrate that inflammatory processes are activated in the early stages of lesion development, even in clinically non-inflamed comedones (*Tanghetti, 2013*).

Emerging evidence has highlighted the crucial role of lipids—particularly sphingolipids—in skin homeostasis, barrier function, and immune signaling. Among these lipids, ceramides (CERs) and sphingosine-1-phosphate (S1P) are of particular

interest due to their dual structural and signaling roles in the skin (**Masuda-Kuroki et al., 2023**). The outermost layer of the epidermis, the stratum corneum, consists of a lipid matrix comprising approximately equimolar concentrations of ceramides, free fatty acids, and cholesterol. This matrix is essential for maintaining skin barrier integrity and hydration, and any imbalance can contribute to dermatological disorders (**Mijaljica et al., 2024**).

Ceramides are sphingolipid molecules composed of sphingosine and fatty acid chains of varying lengths. Long-chain ceramides (C16–C20) and very-long-chain ceramides (C22–C24) have been shown to exert differential effects on keratinocyte behavior and cutaneous inflammation. Specifically, recent data indicate that certain ceramide species play a role in modulating inflammation and cellular proliferation in the skin (**Ho et al., 2022**). For instance, C16 ceramide is often associated with pro-apoptotic and pro-inflammatory effects, whereas very-long-chain ceramides like C24 may contribute to anti-inflammatory functions and promote cell survival. Dysregulation in the balance of these ceramide species can thereby influence the severity and progression of inflammatory skin diseases, including acne vulgaris (**Custodia et al., 2022; Thakkar et al., 2025**). Sphingomyelins (SMs), abundant in both circulation and cell membranes, serve as precursors to ceramides. These SMs can be hydrolyzed by sphingomyelinase (SMase) into ceramides, which in turn can be further metabolized into sphingosine and subsequently phosphorylated into Sphingosine-1-phosphate (S1P) by the action of sphingosine kinase. This conversion pathway is of great interest in inflammatory research (**Thakkar et al., 2025**).

Sphingosine-1-phosphate (S1P) is a potent bioactive lipid that plays diverse roles in immune regulation, angiogenesis, vascular integrity, and inflammatory signaling. In the skin, S1P regulates the behavior of keratinocytes, immune cells, and vascular endothelial cells. It promotes cellular proliferation and survival and can influence immune cell migration and cytokine production. Thus, alterations in serum

or tissue levels of S1P may reflect or contribute to the inflammatory milieu observed in acne vulgaris (*Custodia et al., 2022; Su et al., 2024*).

Although the roles of sphingolipids have been studied in dermatologic disorders such as atopic dermatitis, psoriasis, and ichthyosis, data on their involvement in acne vulgaris remain limited. Most previous studies have focused on skin tissue analyses (*Alizadeh et al., 2023; Delcheva et al., 2024*), whereas investigations into serum sphingolipid profiles—especially ceramides C16, C24, and S1P—in acne patients are scarce. Understanding systemic alterations in these bioactive lipids may provide insights into the inflammatory and metabolic underpinnings of acne vulgaris, potentially identifying novel biomarkers or therapeutic targets.

Aim of the work

1. To measure serum levels of ceramides C16 and C24 in patients with acne vulgaris.
2. To determine the serum level of sphingosine-1-phosphate (S1P) in the same patient group.

Patients and methods

Study approval: The study will be approved by Research and Ethical committee at Faculty of Medicine, Sohag University. Informed written consent will be obtained from all participants after explanation of nature of the study.

Study Design: This is a case-control, cross-sectional, analytical study

Site of the Study: The study will be conducted at the Dermatology Outpatient Clinic in Sohag University Hospitals.

Sample size calculation

The sample size was determined to detect both group differences in serum lipid mediators and correlations with acne severity. Previous work in acne patients (Kaya et al., 2019) included only 30 cases and 20 controls but demonstrated significant lipid alterations. Using standardized effect sizes ($\alpha=0.05$, power 80%), a moderate correlation ($r\approx0.40$) requires ~47 subjects, while a moderate between-group difference (Cohen's $d\approx0.6$) requires ~44 per group. Accordingly, 40 patients and 40 matched controls ($n=80$) .

Study Population:

A. Inclusion Criteria:

For Case Group

This group will consist of (40) patients :

- Both males and females aged 15–40 years.
- Mild, Moderate, severe and very severe cases will be included.

For Control Group:

- This group will consist of age- and sex-matched (40) healthy volunteers.

B. Exclusion Criteria (for both groups):

- Presence of any dermatological condition other than acne vulgaris (for cases).
- Use of systemic or topical treatment such as isotretinoin or antibiotics within the last 3 months.
- Pregnancy or lactation.
- History of lipid-lowering therapy or supplements affecting ceramide or sphingolipid metabolism.

All patients in this study will be subjected to:

1. Clinical Evaluation

A. History including:

- **Demographic data:** Name, age, sex, residence and occupation.
- **History of present illness:**
 - Age of onset of acne.
 - Duration of acne symptoms.
- **Medical History:**
 - Presence of chronic diseases (e.g., diabetes, polycystic ovarian syndrome).
 - Menstrual and contraceptive history in females

B. Dermatological examination:

- **Lesion Assessment:** Documentation of acne lesion types (comedones, papules, pustules, nodules, cysts) Presence of erythema, edema or redness
- **Distribution:** Affected anatomical areas (face, chest, back, shoulders).
- **Scar Evaluation:** Presence and severity of post-acne scarring (atrophic, hypertrophic).

C. Acne Severity Assessment:

Global Acne Grading System (GAGS): It is a system which evaluates acne severity by dividing the face, chest, and back into six regions, each assigned a factor according to its size. The most severe lesion type in each region is graded (0–4), multiplied by the regional factor, and summed to yield a global score (0–44). Severity is then classified as mild, moderate, severe, or very severe. **(Doshi A, 1997)**

The final global score is interpreted as follows:

- 0 → No acne
- 1–18 → Mild acne
- 19–30 → Moderate acne
- 31–38 → Severe acne
- 39–44 → Very severe acne

2. Laboratory Investigation:

Evaluation of Serum Ceramides (C16, C24) and Sphingosine-1-Phosphate (S1P).

a. Sample Collection and Processing:

- **Timing:** Morning samples will be collected after overnight fasting to reduce variability due to dietary lipid intake.
- **Procedure:**
 - A volume of 5 mL of venous blood will be drawn using standard phlebotomy techniques.
 - Blood samples will be allowed to clot at room temperature and then centrifuged at 3000 rpm for 10 minutes.
 - The separated serum will be aliquoted into sterile cryovials and stored at -80°C until analysis to preserve lipid stability.

b. Quantitative Measurement of Lipid Mediators:

- **Method of Analysis:**
- **Quantitative determination of the target sphingolipids will be performed using liquid chromatography coupled with triple quadrupole mass spectrometry (LC-MS/MS) (*Agilent 6460 Triple Quadrupole LC-MS/MS, USA*).**

Procedure:

1. **Add 100 μL serum** into a glass vial.
2. **Add 400 μL methanol** and **200 μL chloroform** (containing internal standards).
3. Vortex for 30 seconds.
4. **Add 200 μL water** and **200 μL chloroform**.
5. Vortex and centrifuge at relative centrifugal force (1000_3000)g for 10 minutes to separate layers.

6. Carefully collect the **lower organic phase** (contains lipids).
7. Evaporate under nitrogen gas at room temperature or using a vacuum concentrator.
8. Reconstitute dried extract in **100 µL of methanol/water (9:1)** with 0.1% (optimized according to instrument condition) formic acid for LC-MS/MS injection .

Statistical Analysis

Data will be statistically described in terms of mean _ standard deviation (SD), median and range, or frequencies (number of cases) and percentages when appropriate. Comparison of numerical variables between the study groups will be done using Kruskal Wallis test. Within group comparison of numerical variables will be done using Wilcoxon signed rank test for paired (matched) samples. For comparing categorical data, Chi square (χ^2) test will be performed. Exact test will be used instead when the expected frequency is less than 5. Correlation between various variables will be done using Spearman rank correlation equation for non-normal variables/non-linear monotonic relation. P values less than 0.05 will be considered statistically significant. All statistical calculations will be done using computer program SPSS

References:

Alizadeh, J., da Silva Rosa, S. C., Weng, X., Jacobs, J., Lorzadeh, S., Ravandi, A., Vitorino, R., Pecic, S., Zivkovic, A., Stark, H., Shojaei, S., & Ghavami, S: Ceramides and ceramide synthases in cancer: Focus on apoptosis and autophagy. *European Journal of Cell Biology*; 2023, 102(3), 151337.

Alsaadoon, N. S. J., Al-Refaie, A. M., & Habashy, A. Y: Acne Vulgaris in Adolescents: A Comprehensive Review. *Benha Journal of Applied Sciences*; 2024, 9(12), 5–13.

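### The protocol calculates about 44 per group and about 47 subjects for 80% power, then adopts 40 per group as if it followed; neither target gets 80%

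*Protocol*

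**What the plan says.** The paragraph headed Sample size calculation (protocol, Patients and methods) gives the study two targets: "The sample size was determined to detect both group differences in serum lipid mediators and correlations with acne severity". With alpha 0.05 and 80% power it reports one requirement for each. A between-group difference of d≈0.6 "requires ~44 per group", and a correlation of r≈0.40 "requires ~47 subjects". The next sentence is the conclusion: "Accordingly, 40 patients and 40 matched controls", a total of 80.

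The inclusion criteria repeat the number for cases ("This group will consist of (40) patients") and give 40 for the healthy volunteers. No reason is offered for going below the calculated figures, and the power is not restated for the number chosen.

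The severity score (GAGS) is part of the clinical evaluation introduced by "All patients in this study will be subjected to". On that scale a score of 0 means no acne.

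**The concern.** The conclusion is worded as a consequence of figures that rule it out: 40 is less than 44, and 40 patients are fewer than 47. The repetition of 40 in the inclusion criteria makes a typing slip unlikely.

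This paragraph is the only calculated support for the size of the study. The earlier study of 30 cases and 20 controls is mentioned as context and supplies no number to the calculation. A reader, or the ethics committee, would take it that the study has 80% power for both targets. If it does not, a null result for a lipid or for its relation to severity carries a higher chance of being a miss than the protocol states.

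**Working it through.** **Inputs.** From the sample size paragraph: alpha 0.05, power 80%, d=0.6, r=0.40, 40 per group. The protocol does not state one- or two-sided; two-sided is taken because only that reproduces its figures (step 2). Normal quantiles: 1.960 (two-sided 0.05), 1.645 (one-sided 0.05), 0.842 (80% power).

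**1. Reproducing the protocol's requirements, two-sided.**

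- Difference: n per group = 2(1.960+0.842)²/0.6² = 2×7.849/0.36 = 43.6, so 44. The noncentral t calculation gives 45.
- Correlation (Fisher z): n = [(1.960+0.842)/atanh(0.40)]² + 3 = (2.802/0.4236)² + 3 = 46.7, so 47.

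Both stated figures are correct.

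**2. Does a one-sided test explain 40?**

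- Difference: 2(1.645+0.842)²/0.36 = 34.3, so 35 (36 by t).
- Correlation: (2.486/0.4236)² + 3 = 37.4, so 38.

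Neither matches 44 or 47, so the protocol's figures are not one-sided.

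**3. Which subjects supply the correlation?** The target is correlation with acne severity. Severity is graded in the patients, and healthy controls would score 0. Severity therefore varies only within the 40 cases, and n=40 applies. This is an inference from the two sections; the protocol does not state it.

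**4. Power at the adopted size, two-sided.**

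- Difference, normal formula: Φ(0.6×√(40/2) − 1.960) = Φ(2.683 − 1.960) = Φ(0.723) = 76.5%. Noncentral t: 75.5%.
- Correlation, Fisher z: Φ(0.4236×√37 − 1.960) = Φ(2.577 − 1.960) = Φ(0.617) = 73.1%. Simulation of the Pearson test: 74.2%.

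**5. Effects detectable with 80% power.**

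- d = 2.802×√(2/40) = 0.626 by the normal formula and 0.634 by noncentral t, so about 0.63.
- r = tanh(2.802/√37) = tanh(0.4606) = 0.43.

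**6. Summary.**

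| Target | Required by the protocol | Adopted | Shortfall | Power at adopted n | Effect at 80% power |
|---|---|---|---|---|---|
| d=0.6 | 44 per group | 40 | 4 per group (4/44 = 9%) | 75.5–76.5% | d≈0.63 |
| r=0.40 | 47 subjects | 40 cases | 7 cases (7/47 = 15%) | 73–74% | r≈0.43 |

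**7. The planned tests.** The Statistical Analysis section plans Kruskal-Wallis and Spearman, not the t-test and Pearson correlation behind 44 and 47. If the data were normal, n=40 would give about 73–74% for Kruskal-Wallis and about 68–71% for Spearman (simulation and large-sample efficiency approximations). The protocol gives no distribution, so these figures only indicate direction: on this assumption the planned tests do not close the gap.

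**The case against.** The strongest counter-argument concerns the correlation. The protocol writes of subjects there and of groups for the difference, and the GAGS scale has a category for no acne. If all 80 participants were correlated, 47 would be exceeded and power for r=0.40 would be about 96%. The text does not exclude this. But putting 40 controls at a score of 0 would mix the case-control contrast into what is meant to be a severity relation, and the protocol grades severity in patients. The case-only reading is the sound one, though it remains an inference. The conflict between 44 and 40 does not depend on it.

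A second argument is precision. Inputs and outputs are marked as approximate, and d≈0.63 and r≈0.43 lie close to d≈0.6 and r≈0.40. It is fair to say that the loss is modest. It is not fair to say that the approximation covers it, because the paragraph itself reports 44 and 47 and these do not round to 40.

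A third is matching. If pairs were matched individually and analysed as pairs, a within-pair correlation of about 0.2 would give about 83% power for d=0.6 with 40 pairs. The protocol, however, states its requirement per group, plans Kruskal-Wallis between groups and gives no within-pair correlation.

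One objection to the remedy stands. Any restated power must name the tests it refers to, because the figures are for a t-test and a Pearson correlation while rank tests are planned.

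**Conclusion.** The concern holds. The adopted 40 per group contradicts the protocol's own requirement of about 44 per group, and this needs no inference. On the case-only reading it also falls short of the 47 needed for the severity correlation. Power is about 4 to 5 points below the stated 80% for the difference and about 6 to 7 points below for the correlation, so the risk of missing the planned effects is about 24.5% and 26–27% instead of 20%.

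These figures assume two-sided testing at 0.05, normal data, an unpaired comparison of equal groups, and severity correlated among the 40 cases. The loss of power is modest. The paragraph still has to be corrected, because it is the only calculated basis for the sample size and its conclusion does not follow from it.

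**What to change.** Keep 40 cases and 40 controls and replace the last sentence of the sample size paragraph with, for example:

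*With 40 cases and 40 controls, two-sided alpha 0.05 and normally distributed data, a t-test has about 75.5% power for d=0.6 and 80% power for d≈0.63. The severity correlation uses the 40 cases only; a Pearson test has about 73% power for r=0.40 and 80% power for r≈0.43. Under normality the planned rank tests have somewhat lower power.*

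The sponsor should confirm the case-only statement, since the protocol is silent on it. The cost is one short passage and a less favourable stated power; no participants are added.

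If the sponsor prefers to keep the 80% claim on the protocol's own basis, 47 cases and 47 matched controls meet both figures (82.1% for d=0.6 by t-test, 80.2% for r=0.40 by Fisher z). That is 94 participants, 14 more than planned. Without 1:1 matching, 47 cases and 44 controls (91 participants, 11 more) give 80.8% for the difference. Even then Spearman would have only about 76–78% power for r=0.40 under normality, so the claim would still have to name the test it refers to.

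### Does the wording of the skin exclusion let volunteers with mild acne into the control group?

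*Protocol*

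**What the plan says.** Under Study Population, the exclusion list is headed "Exclusion Criteria (for both groups" (bracket then closed). Its first item is "Presence of any dermatological condition other than acne vulgaris (for cases" (bracket then closed). The remaining items cover recent systemic or topical treatment, pregnancy or lactation, and lipid-lowering therapy or relevant supplements.

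Controls are described in one line: "This group will consist of age- and sex-matched (40) healthy volunteers". For cases, aged 15 to 40, "Mild, Moderate, severe and very severe cases will be included".

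The procedures section opens with "All patients in this study will be subjected to" and then lists the history, the dermatological examination, GAGS scoring and the blood sampling. The severity scale labels a score of 0 as no acne and 1 to 18 as mild. No GAGS score is tied to eligibility as a control.

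**The concern.** The heading and the tag pull in different directions. If the tag restricts the whole item to cases, controls have no skin exclusion at all. The word healthy is not defined. The examination and GAGS are prescribed for patients, so on a literal reading nobody has to check controls for acne.

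The boundary matters because mild acne is enough to be a case and any score from 1 to 18 is mild. A volunteer with a few comedones could then meet the definition of a case while being counted as a control. The background section also says that "inflammatory processes are activated in the early stages of lesion development, even in clinically non-inflamed comedones", so such a volunteer is not obviously neutral. If affected controls shared part of the acne lipid shift, the case-control difference would shrink towards zero and a real difference could be missed. Controls who were never scored could not be identified later in the analysis.

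**Working it through.** **The text.** The skin item can be read in three ways.

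1. Any skin condition excludes a person from either group, and the tag qualifies only the acne exception, so acne is allowed in cases alone. This agrees with the heading, gives the tag a purpose, and fits the description of controls as healthy.
2. The whole item applies to cases only. This contradicts the heading above it.
3. The item applies to both groups as worded, so acne excludes nobody. This leaves the tag without a function and sits badly with healthy controls in a study that defines its cases by acne.

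Only the first reading reconciles all the text. The tag also stands directly after the acne exception, where a qualifier of that exception would be placed.

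The examination heading points the same way. Blood sampling stands under it. If the word patients excluded controls, no control would be bled and there would be no comparison. The word must therefore be loose there, and it is equally loose for the examination and GAGS under the same heading. The acne-history items do not apply to controls, which makes the heading untidy but does not change the design.

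**The size if the intended reading failed.** The Sample size calculation section gives d = 0.6, r = 0.40, alpha 0.05, power 80% and a planned 40 per group. Its own figures reproduce with a two-sided test:

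- Means: n = 2 × (1.960 + 0.842)² / 0.6² = 43.6, so 44 per group.
- Correlation: n = ((1.960 + 0.842) / atanh(0.40))² + 3 = 46.7, so 47.

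Now let a share f of controls have mild acne with a shift s, while cases have mean 0.6 and the within-group SD is 1. The difference in means becomes 0.6 − f × s. Power was simulated with the Kruskal-Wallis test at 40 per group (40,000 runs per cell), with s = 0.6 (the full case shift) and s = 0.3 (half of it):

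| Share of controls affected (assumed) | Difference, full shift | Power, full shift | Difference, half shift | Power, half shift |
|---|---|---|---|---|
| 0% | 0.60 | 73.5% | 0.60 | 73.9% |
| 10% | 0.54 | 64.0% | 0.57 | 69.2% |
| 20% | 0.48 | 53.2% | 0.54 | 64.2% |
| 30% | 0.42 | 42.7% | 0.51 | 58.7% |

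The two entries at 0% differ only by simulation error. At half shift the loss is 73.9 − 69.2 = 4.7 points at 10% and 73.9 − 64.2 = 9.7 points at 20%. Fixing the number of affected controls instead of drawing it at random gives 73.2 − 68.7 = 4.5 and 73.2 − 63.7 = 9.5 points.

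A t-test calculation for the full shift, with effective d = 0.6(1 − f) / √(1 + 0.36 f(1 − f)/2), gives 75.5%, 65.8%, 55.2% and 44.5%, the same pattern. Power is below 80% even with clean controls because 40 per group is used where 44 was calculated. That is a separate matter and not part of this loss.

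**The price of a strict rule.** To enrol 40 controls with GAGS 0, the number to screen is 40 / (1 − f): 44.4, 50.0 and 57.1, so 45, 50 and 58 volunteers at 10%, 20% and 30% affected.

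**The case for a change.** The strongest case for a change is that control eligibility belongs in the protocol, and that healthy does not plainly exclude a few comedones. The other exclusions would catch recently treated acne but not untreated mild acne. The grading form is already in use, scoring controls takes minutes, and a misclassified control who was never scored cannot be recovered afterwards.

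Part of this stands. The item is clumsily worded, healthy is undefined, and the protocol does not say how acne-free status is confirmed. The rest is weaker. Nothing in the text shows that controls with acne are intended, and recruitment runs from a dermatology clinic where visible acne is unlikely to pass unnoticed. The background sentence on comedones concerns inflammation during lesion development, not serum C16, C24 or S1P, and the protocol itself calls serum data in acne scarce. The full-shift losses assume that a few comedones move serum lipids as far as the average of a mild-to-very-severe case group, which fits poorly with the correlation with severity that the study is sized to detect.

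Requiring GAGS 0 is also a debatable choice. It adds screening and makes controls cleaner than the general population of that age. A looser rule of no clinical acne at examination would be equally defensible.

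**Conclusion.** No change to the plan follows. The heading, the position of the tag and the description of controls support one reading under which controls have no skin condition, acne included, and the comparison is sound. What remains is loose wording and an unstated check that a dermatology clinic would carry out as a matter of course.

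The loss arises only if that reading fails in practice and acne in controls goes unnoticed. It is then about 5 points of power at 10% of controls affected and 9 to 10 points at 20%, assuming d = 0.6, 40 per group and half the case shift in mild acne. The full-shift losses, about 10 and 20 points (73.5 − 64.0 = 9.5 and 73.5 − 53.2 = 20.3), are an upper bound. The protocol gives neither the rate of acne among volunteers nor the serum shift in mild acne, so these figures illustrate and do not estimate. Affected controls who share the case shift would hide a difference rather than create one. For other skin diseases in controls the protocol gives no serum direction, so none is claimed.

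### Minor: controls are matched on age and sex, but the fixed case-control test uses neither factor; rank regression on group, age and sex costs almost nothing and may recover some power

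*Protocol*

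**What the plan says.** Under Study Population, the control group is defined by matching: "This group will consist of age- and sex-matched (40) healthy volunteers". Whether the matching is individual or by frequency is not stated. Cases are of both sexes and aged 15 to 40.

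Under Statistical Analysis, the between-group test is fixed: "Comparison of numerical variables between the study groups will be done using Kruskal Wallis test". The protocol mentions no covariate, stratum, case-control pairing or regression for this comparison.

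The one test described for matched data is given a different job: "Within group comparison of numerical variables will be done using Wilcoxon signed rank test for paired (matched) samples".

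Under Sample size calculation, a standardized difference of about 0.6 at 5% significance and 80% power "requires ~44 per group", while 40 per group are planned.

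Age and sex are already recorded for patients; the history lists "Name, age, sex, residence and occupation". For controls they must be known, or matching could not be done.

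**The concern.** Matching makes the two groups alike in age and sex. If these factors influence serum ceramides or S1P, the difference between the groups varies less from study to study than it would with unmatched groups. Kruskal-Wallis takes its null variance from the total spread of the pooled ranks, which still contains the age-sex part. The denominator is then too large for the design: true type I error falls below 5% and power is lower than the same 80 samples could give.

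Only precision is at stake. The planned test does not bias the comparison. The protocol names a specific test here, so this is a stated choice and not a detail left to an analysis plan.

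**Working it through.** **Inputs.** From the protocol: two groups of 40, d = 0.6, α = 0.05 (two-sided, which reproduces the stated size), power 80%, ages 15 to 40, matching on age and sex. Assumed, because the documents do not give it: s, the share of within-group lipid variance explained by age and sex.

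**1. The plan's own figure.** n = 2(1.960 + 0.842)² / 0.6² = 43.6, so 44 per group. This reproduces the protocol. At 40 per group, d√(n/2) = 0.6 × √20 = 2.683, and power = Φ(2.683 − 1.960) = 76.5%. The t test gives 75.5%. Kruskal-Wallis gives 74.6% using its relative efficiency of 0.955, and about 73 to 74% in simulation.

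**2. Why the unadjusted test is conservative.** With total variance 1, the test assumes that the difference has variance 2/n. With age and sex balanced by matching, its actual variance is about 2(1 − s)/n. On the normal approximation:

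- unadjusted type I error = 2[1 − Φ(1.960/√(1 − s))]
- unadjusted power = Φ((2.683 − 1.960)/√(1 − s))
- adjusted power = Φ(2.683/√(1 − s) − 1.960)

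| s | Unadjusted type I error | Unadjusted power | Adjusted power | Gain (points) |
|---|---|---|---|---|
| 0 | 5.0% | 76.5% | 76.5% | 0 |
| 0.10 | 3.9% | 77.7% | 80.7% | 3.0 |
| 0.20 | 2.8% | 79.1% | 85.1% | 6.0 |

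These gains are a best case: they assume that the matching is complete and that the model captures the whole age-sex effect. The power levels are for a comparison of means; rank tests sit a little lower.

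**3. Simulation with the tests themselves, linear age effect.** 20,000 studies per cell; normal data; age uniform on 15 to 40; sexes 1:1; s split equally between age and sex; matching on sex and 5-year age band. Monte Carlo error is about 0.3 points for power.

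| s | Kruskal-Wallis power | Rank regression power | Kruskal-Wallis type I | Rank regression type I |
|---|---|---|---|---|
| 0 | 73.6% | 73.7% | 5.2% | 5.2% |
| 0.05 | 73.8% | 75.3% | 4.6% | 5.1% |
| 0.10 | 74.4% | 77.6% | 3.8% | 5.1% |
| 0.20 | 75.8% | 82.2% | 2.8% | 4.9% |

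Pairwise matching within two years of age (10,000 studies per cell) gives 73.0/73.1% at s = 0, 74.5/77.7% at 0.10 and 74.9/82.0% at 0.20. Frequency matching agrees within about a point, so the result does not depend on which kind of matching is meant.

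**4. The same comparison when the age effect is not linear.** With a U-shaped age effect and only a linear age term in the model (8,000 studies per cell), Kruskal-Wallis against rank regression is 73.8/75.6% at s = 0.10 (gain 1.8) and 75.7/78.8% at s = 0.20 (gain 3.1). If all of s is U-shaped age, the gain is only about 0.1 to 0.3 points. Adding age squared recovers the gain when the effect is curved and cost nothing measurable when it is not.

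**5. Cost when age and sex do not matter.** For the t-based comparison at s = 0, two extra covariates change power from 75.50% to 75.47%.

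**The case against.** The strongest reply is that nothing here is wrong. A rank comparison of groups balanced by design is valid, and adjustment may buy nothing: no sentence in the protocol says that age or sex predicts C16, C24 or S1P. Even if they do, the larger gains require an age effect of the shape that the model fits. An adjusted analysis could also appear in a separate analysis plan, and a rank coefficient tells the reader less than a difference in serum level.

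Most of this stands, and it sets the size of the point. It does not remove it, because the change is nearly free, uses data already held and was not materially worse than the planned test in any setting examined.

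Three stronger readings are tempting, and the documents support none of them.

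- **That ignoring the matching biases or invalidates the comparison.** The error runs the other way: type I error is at or below about 5%.
- **That adjustment makes up for planning 40 per group when the calculation gives 44.** Adjusted power reaches 80% only at s near 0.15 with a linear age effect, and the protocol supports neither condition. The 44 against 40 discrepancy is a separate matter.
- **That a paired test is required, or was intended, for cases against controls.** Individual pairs are never described. The signed-rank sentence refers to a within-group comparison that it does not name. The introduction's remark on "Dysregulation in the balance of these ceramide species" might suggest C16 against C24 in the same person, but the protocol does not say so. That is a question of wording and no part of this point.

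**Conclusion.** The point holds as a minor, inexpensive improvement. The fixed test is valid, but conservative if age and sex predict the lipids. At 40 per group and d = 0.6, the power forgone is nil at s = 0, about 0 to 3 points at s = 0.10 and about 0 to 7 points at s = 0.20. Both s and the shape of the age effect are assumptions. The upper ends need an age effect that is roughly linear, or a curved one modelled with age squared; the lower ends apply to a curved effect fitted with a straight line. The safe statement is that adjustment can help and costs next to nothing, not that it secures any particular power.

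**What to change.** In Statistical Analysis, replace the between-group test for C16, C24 and S1P with a linear regression of the rank of the lipid on group, age and sex, optionally with age squared. Settle the terms before the lipid data are seen. Keep reporting medians and ranges by group, since the rank coefficient has no natural unit.

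This takes one sentence, no new data and no extra participants. SPSS, the named software, can rank a variable and fit the model. It works under individual or frequency matching, needs no pair identifier and keeps every usable sample.

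The alternatives have costs:

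- Regression of the log lipid gives an interpretable effect, but with heavy-tailed data (t with 5 degrees of freedom) and s = 0 its power was 76.2% against 83.1% for Kruskal-Wallis.
- A signed-rank test on case-control pairs is possible only if matching is individual, and it drops a pair for each failed sample. With two control samples lost, power was 70.5% on 38 pairs against 72.4% for rank regression on 78 people at s = 0, and 79.5% against 81.1% at s = 0.20 with a linear age effect.

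As a separate clarification of wording, name the comparison that the within-group signed-rank sentence serves, or delete it.
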